**Baseline/Enrollment Visit Week 1.** The first visit begins with the final set of screening assessments: CO > 3ppm and negative pregnancy test for female participants. Once the screening is complete, participants who remain eligible will start the consent process. Staff describe the study, answer all questions, ensure understanding of the study information, and re-assess interest in participating. Participants who remain interested will be asked to sign the informed consent form. Participants will complete the baseline questionnaire on a tablet, and participants will have vital signs taken (blood pressure, heart rate, height, weight). Participants will also be trained on the EMA protocol (see below for more details) and given instructions to go home and smoke as they usually do. **The purpose of this first EMA week is to provide baseline data about the participant's smoking pattern which will be compared to their SREC/cigarette use pattern after switching.**

**Week 2 Visit.** Participants will complete a brief questionnaire and complete an expired CO assessment. Study staff conduct a debriefing interview to review the EMA week and their compliance with the protocol. Participants will be randomly assigned to the two flavor conditions, stratifying for gender. Those participants assigned to the choice condition will select from four SREC flavors (tobacco, menthol, watermelon, and blueberry) based on their preference. Participants assigned to the usual flavor condition will receive tobacco pods if they smoke regular cigarettes and menthol pods if they smoke menthol cigarettes. Participants in both conditions will receive **brief behavioral counseling** (see below for more details) on reducing their combustible cigarette use and using SREC as a substitution for cigarettes. Starting this week, participants begin to receive daily email or text prompts (based on participant's preferred mode of communication) to complete a brief online survey on their use of cigarettes, SREC, and non-SREC e-cigarette use each day.

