## **6.1. Behavioral Intervention**

Participants in both conditions will receive brief behavioral counseling on several cigarette reduction strategies, including substitution of cigarettes with the SREC. Participants will be told to carry the SREC with them as they would their cigarettes, and to use the SREC when they feel the urge to smoke. Participants will

be told that it may take a few days to adjust to the SREC and a pattern of use, but that each day they should try to reduce the number of cigarettes smoked. Once participants have a week of experience with the SREC, they will be encouraged not to carry their usual cigarettes with them as another strategy of reducing their cigarette use. Staff will work with participants to set individual goals for reduction during this first week, with the goal of achieving at least 75% reduction in the number of combustible cigarettes smoked by the end of the week, and all encouraged to reduce further. Participants will be told that they should strive for complete switching after the first week. Participants will also be told not to use any other tobacco or nicotine products during their participation in the study.

The behavioral intervention is based on [name] prior work on a recently completed clinical trial evaluating treatment components to help smokers who were unmotivated to quit, to reduce and to attempt to quit. This treatment included a behavioral reduction component, which focused on strategies to help smokers systematically cut down on cigarettes. We are adapting this brief behavioral intervention by also providing coaching on how to use the SREC as a replacement for some cigarettes throughout the day.

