Adverse Events (e.g., throat irritation, nausea)			x	X	x	x	x	x	x	x	x	x	x	x		

A. A **Comprehensive questionnaire** (baseline and 14-Week End of Treatment visits) will be completed in-person to assess key constructs [e.g., sociodemographics, tobacco and nicotine use (history, dependence, attitudes, motivations, intentions, perceived harm), tobacco environment, cessation history and intentions, and other substance use]. Each questionnaire will take approximately 30 - 40 minutes to complete. Shorter **brief surveys** (5-7 minutes to complete) will be completed at weeks 2, 3, 4, 6, 8, and 11. These measures serve as important descriptors of our sample, serve as covariates or moderators in our analyses, and serve as predictors of success in reducing cigarettes and switching to SREC over time.

B. A **daily use survey** completed online via REDCap from an emailed or texted survey link starting at the week 2 visit through the week 14 visit (over the 12 treatment weeks) to assess the use of cigarettes, SREC, and any other e-cigarette/nicotine vaporizer. Each of these surveys will take about 1 minute to complete. This brief survey will serve as an indicator of change in patterns of use as well as a way for the Clinical Interviewer Staff to track progress with cigarette reduction and to monitor nicotine exposure during the treatment phase. Daily surveys ask about the number of cigarettes smoked and the number of SREC or other e-cigarette episodes on the previous day (an episode is defined as 15 puffs or a period lasting about 10 mins). We also ask if the participant finished a pod on the previous day.

C. **Two, week-long waves of EMA data collection** using a **study provided smartphone**, the first wave will take place immediately following completion of the baseline questionnaire (week 1 visit through week 2 visit), and the second wave will take place starting at the week 3 visit through the week 4 visit. The first week of EMA provides the baseline comparison with combustible cigarettes to the second EMA wave when participants will have one week of experience with using the SREC and some practice cutting down on their cigarette smoking. Each EMA wave will cover 7 consecutive days, ensuring both weekday and weekend sampling.

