## 9.0 Data Analysis

**Aim 1. Examine whether conventional cigarette smokers can significantly reduce their combustible cigarette use by switching to SREC.** We will have assessments of the amount of SREC and combustible cigarettes used every week for 12 weeks. SREC/e-cigarette use per day is captured by the total number of e-cigarette episodes defined as about 15 puffs or a period lasting about 10 minutes. Both of these outcomes will be modeled as count data (average # cigs/day and SREC episodes/day for each week) using a mixed-effects Poisson regression model (or Negative Binomial model if the Poisson assumption of equality of mean and variance is not met). In these analyses, we will examine primarily linear and curvilinear changes across time using orthogonal polynomial transforms, in order to assess the independent effects of these two types of trends, which will be treated as random effects to allow heterogeneity across subjects in the time trends. These time trend analyses will allow us to investigate the **sustainability of reductions in cigarette use and changes in SREC use**. In addition to the effect(s) of time, the main independent variable is group (usual flavor or flavor choice). Although we expect the group effect to be consistent across the 12 weeks, we will test whether the group effect varies across time (i.e., group by time interaction). For example, it may be likely that differences between the groups increase over time if the usual flavor group more rapidly relapses back to smoking cigarettes and gives up on their SREC. Our primary endpoint will be the model-based estimate of the group difference at the final 12-week timepoint (study week 14). We will also consider the proportion of participants who achieve total abstinence from combustible cigarettes at the end of the 12-week trial (defined as no cigarette smoking in the past 7 days and confirmed by CO < 3 ppm; see power section). Although our primary endpoint is the end of the 12 weeks of treatment, (week 14) we will also evaluate effects at the one-month follow-up. In terms of these primary outcomes, we will further examine the degree to which

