group differences are moderated by gender, baseline menthol cigarette use (not SREC flavor), and nicotine dependence level, and also examine the degree to which baseline characteristics might predict success on these outcomes. We will use descriptive statistics to report the frequency of flavor choice, how that varies over time, by condition, and by level of reduction.

We will also be weighing all returned SREC pods and will also be able to develop a measure of SREC use per week based on SREC pod weight.

**Aim 2. Examine whether reductions in conventional cigarette use and uptake of SREC are associated with changes in health and biomarker variables.** Smokers may vary in how completely they substitute SREC for their conventional cigarettes. Thus, for each participant, we will have, on a weekly basis, the number of cigarettes smoked and the number of SREC episodes or returned SREC pod weights. As indicated above, these will be modeled using mixed models for counts, which yield empirical Bayes estimates for each subject of their change across time in cigarette and SREC usage. We will examine how these change in usage estimates are associated with changes in the following variables: 1) CO level; 2) blood pressure; 3) heart rate; 4) weight (assessed baseline and at end); 5) self-report of respiratory symptoms (baseline and at end); and 6) nicotine dependence (assessed at baseline and end). For each of these continuous outcomes, we will use linear mixed models with effects of time and group (usual flavor or free choice), and group by time interaction if significant. To these models, we will add in the empirical Bayes estimates of cigarette and SREC change (obtained from the stage 1 mixed models for counts) and specifically examine the change by time interactions (and change by group by time if the group by time interaction is significant). As the empirical Bayes estimates from the stage 1 analyses have uncertainty attached to them, we will use the resampling approach advocated by Tsonka et al for using empirical Bayes estimates from a first stage analysis as covariates in a second stage model.

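### As described, Aim 2's change-in-use covariate is a trend within the 12 treatment weeks with no pre-switch level, so it understates and misranks people who cut down early

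*Combined protocol and SAP*

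**What the plan says.** Aim 2 in Section 9.0 is a two-stage analysis. Stage 1 reuses the Aim 1 mixed models for counts, "which yield empirical Bayes estimates for each subject of their change across time in cigarette and SREC usage". Stage 2 enters those estimates in linear mixed models for CO, blood pressure, heart rate, weight, respiratory symptoms and dependence, to "specifically examine the change by time interactions". A resampling step carries the stage 1 uncertainty forward.

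For stage 1, the Aim 1 text states: "We will have assessments of the amount of SREC and combustible cigarettes used every week for 12 weeks". Time enters as "linear and curvilinear changes across time using orthogonal polynomial transforms", with random effects. Section 6.3 shows that the daily survey runs "starting at the week 2 visit through the week 14 visit (over the 12 treatment weeks"), so it begins when SREC is first dispensed. No baseline occasion, offset or baseline covariate is named.

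The outcomes start earlier. Section 9.0 lists "self-report of respiratory symptoms (baseline and at end"), with weight and dependence on the same two occasions. Table 2 has CO, blood pressure and heart rate from week 1. Section 6.1 sets individual goals for the first SREC week, "with the goal of achieving at least 75% reduction in the number of combustible cigarettes smoked by the end of the week", and complete switching after that. Pre-switch smoking is recorded: in Section 6.0, under the week 1 visit, "The purpose of this first EMA week is to provide baseline data about the participant's smoking pattern", and Table 2 marks daily use at week 1.

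**The concern.** The exposure and the outcome cover different intervals. The outcome change runs from before the switch to week 14. The exposure change runs from the first SREC week to the twelfth, although the intervention is built to produce most of the reduction inside that first week. The stage 1 intercept does carry each person's level of use, but Aim 2 names the change estimates, and level without baseline would confuse light smokers with reducers, since entry starts at 3 cigarettes a day.

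The Aim 2 hypothesis is that more complete substitution brings larger falls in CO and respiratory symptoms. If the covariate mainly measures what happens after the initial drop, a true association is diluted and a null result is hard to interpret. Resampling deals with imprecision in the estimate, not with an estimate of the wrong quantity. SREC has the same problem: someone who takes it up at once and uses it steadily shows no trend.

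**Working it through.** **1. The plan's own figure.** Section 12.0 gives a detectable r = 0.262 at power 0.8, two-tailed, with 120 × 0.9 = 108 participants. Alpha of 0.05 is stated under Aim 4 and assumed here. The noncentral t test gives power 0.798 at r = 0.262, so the figure reproduces. By Fisher z: atanh(0.262) × √105 = 0.268 × 10.247 = 2.749, and Φ(2.749 − 1.960) = 0.785. Later powers use Fisher z and should be compared with 0.785.

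**2. What the stage 1 trend gives known profiles.** Inputs: 11 and 15 cigarettes/day (Section 12.0) and the 75% target (Section 6.1). For a linear ramp over the first week, the rate on day d is 1 − 0.75·d/7 of baseline. The week's mean is 1 − 0.75 × 4/7 = 4/7, that is 6.29 from a base of 11 or 8.57 from 15. Later weeks are 2.75 or 3.75. The Poisson trend log μ = a + b·week is fitted to noise-free weekly means. Gradual changes are straight lines in cigarettes/day. The slopes are the same for both bases; levels below are for base 11.

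| Profile | First week → twelfth week | b, 12 weeks only | b, baseline point added |
|---|---|---|---|
| No reduction | 11 → 11 | 0 | 0 |
| Immediate 75% cut, held | 2.75 → 2.75 | 0 | -0.082 |
| Ramp to 75% in first week, held | 6.29 → 2.75 | -0.045 | -0.104 |
| Slow 40% cut | 11 → 6.6 | -0.046 | -0.043 |
| Gradual 75% cut | 11 → 2.75 | -0.112 | -0.104 |
| 75% cut drifting back to 50% | 2.75 → 5.5 | +0.061 | -0.0065 |

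Over 11 weekly steps the ramp profile's fitted ratio is exp(11 × −0.0449) = 0.61, against a true 0.25 from baseline. The drifting profile ends at half of baseline but gets a fitted ratio of 1.96.

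**3. The curvilinear term.** With linear and quadratic terms, the ramp profile gets about -0.039 and +0.015. The non-reducer and the immediate sustained cutter both get 0 and 0, so curvature does not separate those two.

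**4. Dilution under assumed variances.** In a simulation of 108 people, empirical Bayes slopes from a Poisson random-intercept-and-slope model were correlated with the true log change from baseline, under four assumed settings for later drift. None of the variances comes from the documents.

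| Scenario | Linear, 12 weeks | Linear + quadratic, 12 weeks | Linear, baseline added |
|---|---|---|---|
| Ramp in first week | 0.787-0.935 | 0.797-0.943 | 0.843-0.976 |
| Full drop at once | 0.111-0.828 | 0.753-0.914 | 0.801-0.971 |

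Suppose the outcome depends on use only through true change from baseline. The observable correlation is then 0.262 times the factor shown. Ramp, linear term: 0.262 × 0.787 = 0.206, power 0.573; 0.262 × 0.935 = 0.245, power 0.727. Immediate drop, linear term: 0.262 × 0.828 = 0.217, power 0.62 at best; at the low end, 0.262 × 0.111 = 0.029, power 0.06, hardly above the test level.

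**The case against.** Several points against the concern stand.

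- A reader might infer that the reduction happens before the modelled series. The documents do not support that. SREC, counselling and daily reports all start at the week 2 visit, and the goal is for the end of that week, so the first weekly mean contains the ramp.
- A reader might infer that 75% reducers in general get the same value as non-reducers. That is exact only when the whole drop is in place from the start of the first SREC week and then stays flat.
- Much larger power losses can be produced by placing the whole drop outside the series. With an assumed SD of 0.8 for the log drop and 0.5 for the later trend, the correlation of trend with total change is (0.25 + 0.4c) / (0.5·√(0.89 + 0.8c)), where c is the correlation of drop and trend. It is 0.53 at c = 0, 0.14 at c = -0.5 and 0.79 at c = +0.5. Neither the SDs nor c comes from the documents, and the set-up contradicts the start of the series, so a collapse in power or a reversal of sign is not established.
- The 0.262 is stated for SREC use and health outcomes. Applying it to cigarette change is an illustration.
- CO, blood pressure and heart rate are measured at eight visits, six of them after SREC starts (weeks 3, 4, 6, 8, 11 and 14). A within-treatment trend is partly matched to those outcomes. The mismatch is sharpest for weight, symptoms and dependence.
- The plan does not expressly exclude baseline use from stage 1. Its absence is inferred from the described window and data source.

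What this leaves untouched: followed as written, the covariate is a within-treatment trend, and on the protocol's own target path it scores a 75% reducer like a slow 40% cutter.

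**Conclusion.** The point holds as a should-fix. The understatement and misranking follow from the described time window and need no variance assumption: -0.045 against -0.046 per week for two very different reducers, +0.061 for someone at half of baseline, and 0 for both an immediate sustained cutter and a non-reducer. The loss of power does rest on assumptions: about 0.57-0.73 against 0.785 for the ramp case, and less if the drop is immediate and only the linear term is used. With curvature included, the immediate-drop correlations are 0.75-0.91, so the lowest figures belong to the linear trend alone. Aim 2 is associational, and the primary endpoint, the group difference at study week 14, does not use this covariate. The stated 0.262 is not itself wrong; it assumes that the intended change is observed directly at one timepoint.

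**What to change.** State in Section 9.0 that the cigarette covariate is change from the pre-switch baseline. There are two workable routes: add the week 1 rate to stage 1 as a baseline occasion with its own baseline-to-treatment step, or pair each person's model-estimated end-of-treatment level with the baseline rate. Adding baseline merely as one more point on a straight line is not enough: the profile that drifts back from 75% to 50% would still get only -0.0065 per week. For SREC, use the estimated treatment-period or week-12 level, since study use starts at zero. Keep the resampling step.

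No new data are needed, but the wording has to settle two matters. Baseline smoking comes from EMA or the questionnaire and later use from the daily survey, so part of any step could reflect the instrument; name the baseline measure and check sensitivity to the alternative. A raw log change is undefined at zero cigarettes, which is where complete switchers are, so use model-based estimates or proportional reduction. The latter stays finite because entry requires at least 3 cigarettes a day. A single baseline occasion also limits how precisely each person's step is estimated. The cost is a paragraph in the plan and one sensitivity analysis, best settled before the data are analysed.

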E. **Carbon-monoxide (CO) level** in expired air will be measured using a digital monitor at each study visit allowing us to examine changes in CO over time along with changes in patterns of cigarette and SREC use. There are no required qualifications or credentials for the use of a carbon monoxide (CO) monitor. It is a very basic device that simply requires a subject to exhale into a disposable (single use), mouthpiece attached to the digital monitor. All staff involved in the implementation will be trained in the protocol, which includes the following:

1. A member of the research staff will insert a new mouthpiece, turn the monitor on and hand the monitor to the participant.
2. The participant will be instructed to inhale, hold the breath for 15 seconds, and then exhale the entire breath through the mouthpiece into the digital monitor while following the on-screen prompts.

F. **Urine pregnancy tests** will be administered to female participants of childbearing age (defined as 55 years old and younger) during the Week1/Enrollment visit and every 5 to 6 weeks during the study; those with positive test results (a result indicating pregnancy) will be removed from the study.

G. Other **vital signs** will be measured at study visits including height and weight (baseline and end of treatment), blood pressure and pulse (at every study visit).

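### Aim 2 health outcomes: if group-by-time is dropped as non-significant, the remaining group effect mixes pre- and post-randomisation readings and understates a week-14 arm difference

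*Combined protocol and SAP*

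**What the plan says.** Section 9.0, Aim 2, sets its target as an association: "We will examine how these change in usage estimates are associated with changes in the following variables". The model for each continuous health outcome is given as: "we will use linear mixed models with effects of time and group (usual flavor or free choice), and group by time interaction if significant". Individual estimates of change in cigarette and SREC use are then added, and the analysts will "specifically examine the change by time interactions (and change by group by time if the group by time interaction is significant").

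On timing, the same paragraph lists "4) weight (assessed baseline and at end); 5) self-report of respiratory symptoms (baseline and at end") and "nicotine dependence (assessed at baseline and end"). Section 6.3, item E, says that expired CO "will be measured using a digital monitor at each study visit allowing us to examine changes in CO over time". Table 2 places CO and vital signs at weeks 1, 2, 3, 4, 6, 8, 11 and 14, and the respiratory questionnaire (SGRQ) at weeks 1, 14 and 18.

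Section 6.0 puts randomisation and the first SREC supply at the week 2 visit, where "Participants will complete a brief questionnaire and complete an expired CO assessment". Readings at weeks 1 and 2 therefore precede any possible arm effect.

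For cigarettes per day, Section 9.0 (Aim 1) commits to a model-based group difference at study week 14. No equivalent commitment is made for the health outcomes. Nothing in the Aim 2 text makes baseline a covariate or sets the arms equal before randomisation.

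**The concern.** Group-by-time is the term that separates the arms after randomisation. If it is dropped, the model assumes one arm difference common to all readings, including those taken when the true difference is zero by design. The coefficient is then pulled toward zero, and it also absorbs part of any chance difference between the arms at baseline.

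The significance of one test thus decides which quantity is reported: a difference in change, or a diluted average level. A reader shown the second as the effect of flavor choice on weight, dependence or respiratory symptoms would see too small a number. The same test also decides whether the three-way term with usage change is examined.

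**Working it through.** **1. The plan's own Aim 2 figure.** Section 12.0 states power .8 for a correlation of .262 with 108 participants, two-tailed. With alpha 0.05 (stated for Aim 4, assumed here), Fisher's z gives atanh(.262) × √105 − 1.96 = 0.79, so power 0.785; the noncentral t gives 0.798. The figure reproduces. It concerns the association, and the plan states no power for an arm difference in these outcomes.

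**2. Inputs.** From the documents: 54 per arm at the end, and the reading times above. Assumed, because the documents give no SD or correlation for these outcomes: equal variances, one common within-person correlation ρ, and the effect sizes used below. Blood pressure and heart rate follow Table 2 and Section 6.3, item G (every visit); Table 1 lists vitals only at weeks 1 and 14. Section 9.0 does not say whether both the week 1 and week 2 readings are outcome rows; I take it that they are.

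**3. What the fallback coefficient estimates.** With complete data and a constant post-randomisation effect, it estimates the effect × (post readings ÷ all readings). The last column gives the mean estimate over 150 simulated trials with a true difference of 0.5 SD, fitted by mixed model.

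| Outcome | Pre / post | Fraction | Expected | Simulated (SE) |
|---|---|---|---|---|
| Weight, dependence, respiratory symptoms (weeks 1 and 14) | 1 / 1 | 1/2 | 0.25 | 0.23 (0.014) |
| Same, 10% missing at week 14 | 1 / 1 | – | – | 0.21 (0.014) |
| Respiratory symptoms with week 18 | 1 / 2 | 2/3 | 0.33 | 0.34 (0.014) |
| CO, blood pressure, heart rate | 2 / 6 | 3/4 | 0.375 | 0.38 (0.012) |

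**4. How often the fallback is reached: two-reading outcomes.** Variances in SD² units, each multiplied by 2/54:
- baseline-adjusted week-14 comparison: 1 − ρ²
- group-by-time (difference in change): 2(1 − ρ)
- group main effect: (1 + ρ)/2

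Set the effect so that the baseline-adjusted test has power 0.80, that is effect/SE = 1.96 + 0.84 = 2.80. With 54 per arm this is 0.47 SD at ρ = 0.5 and 0.39 SD at ρ = 0.7. Then:
- Interaction: effect/SE = 2.80 × √((1 + ρ)/2) = 2.43 at ρ = 0.5 and 2.58 at ρ = 0.7. Power is 0.68 and 0.73, so the term is dropped in 32% and 27% of trials.
- Fallback main effect: estimate/SE = 2.80 × √((1 − ρ)/2) = 1.40 and 1.09. Power is 0.29 and 0.19.

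At ρ = 0.9 on the same calibration the interaction has power 0.78, so it is dropped in about 22% of trials.

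**5. The same question at fixed effects.** The interaction is dropped in 45%, 24% and 0.4% of trials at 0.4 SD for ρ = 0.5, 0.7 and 0.9, and in 26%, 8% and under 0.1% at 0.5 SD. In a simulation of the test-then-drop rule at 0.5 SD, the group coefficient among trials that dropped the term averaged 0.25 SD at ρ = 0.5 and at ρ = 0.7, which is again half.

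**6. CO.** On the calibration of step 4, now with the mean of weeks 1 and 2 as baseline and a constant effect from week 3, the group-by-time test has power 0.69-0.72 if time is linear, 0.84-0.86 with categorical visits, and about 0.98 as a pre/post contrast, for ρ = 0.5-0.7. Section 9.0 does not say how time is coded in these models. The fallback main effect has power 0.63 at ρ = 0.5 and 0.36 at ρ = 0.7.

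**The case against.** The strongest reply is that Aim 2 does not set out to compare arms. Its hypothesis concerns completeness of substitution, its power is stated for a correlation, and its change-by-time terms are fitted whatever the interaction test shows. Group is mainly an adjusting term. This stands, and it limits the weight of the point.

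A second reply is that the plan already contains an undiluted arm comparison. The group-by-time term is tested, and with one reading before and one after it is exactly the arm difference in change. This also stands. A reader might infer from the model sentence that the averaged group effect is the only arm comparison of the health outcomes, and so that every real difference is halved. The documents do not support that: the interaction is kept when significant, which is the more frequent result under the step 4 assumptions. The like-for-like loss of power for the two-reading outcomes is from 0.80 to 0.68-0.73; the 0.19-0.29 belongs to the fallback alone.

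A reader might also infer that a real CO benefit is likely to be missed. That is not shown. Two of the three time codings in step 6 exceed the 0.80 of a baseline-adjusted week-14 test, and Section 9.0 also compares the arms on CO-confirmed abstinence at the end of treatment.

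These replies do not meet the remaining problem. When the test fails, no undiluted estimate is promised, and the coefficient left in the model answers a different question.

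**Conclusion.** The point holds in conditional form. When group-by-time is non-significant and removed, the group coefficient estimates about half of a week-14 difference for weight, dependence and respiratory symptoms (two thirds for the last if week 18 is used), and about three quarters of a constant effect for CO, blood pressure and heart rate if weeks 1 and 2 are both outcome rows. For the two-reading outcomes this happens in about 27-32% of trials when ρ is 0.5-0.7 and the effect is one that a baseline-adjusted week-14 test would detect with power 0.80. Those correlations and effects are assumptions, and the frequency moves widely with them (step 5); the fractions follow from the reading schedule. The point is secondary because the usage-health associations are the aim's target. I rate it a cheap improvement.

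**What to change.** In Section 9.0, Aim 2:
- Treat the week 1 and week 2 readings as baseline, either by giving the arms a common pre-randomisation mean or by using baseline as a covariate. The common-mean form keeps the baseline rows that the change-by-time terms need for two-reading outcomes; the covariate form would need a separate model for the arm contrast.
- Keep group-by-time whatever its p-value, and state how time is coded.
- Report any arm difference in a health outcome as the week-14 contrast, as Aim 1 does for cigarettes per day.
- Reconcile the respiratory-symptom timing in Section 9.0 (baseline and end) with Table 2 (also week 18), and say whether week 18 enters the model.

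The cost is SAP wording and a few extra model parameters. No visit, measurement or sample size changes.
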